Type # (1-5)	Description of Ideation	Most Severe																		
Frequency How many times have you had these thoughts?	(1) Less than once a week (2) Once a week (3) 2-5 times in week (4) Daily or almost daily (5) Many times each day	—																		
Duration When you have the thoughts how long do they last?	(1) Fleeting - few seconds or minutes (4) 4-8 hours/most of day (2) Less than 1 hour/some of the time (5) More than 8 hours/persistent or continuous (3) 1-4 hours/a lot of time	—																		
Controllability Could/can you stop thinking about killing yourself or wanting to die if you want to?	(1) Easily able to control thoughts (4) Can control thoughts with a lot of difficulty (2) Can control thoughts with little difficulty (5) Unable to control thoughts (3) Can control thoughts with some difficulty (0) Does not attempt to control thoughts	—																		
Deterrents Are there things - anyone or anything (e.g., family, religion, pain of death) - that stopped you from wanting to die or acting on thoughts of committing suicide?	(1) Deterrents definitely stopped you from attempting suicide (4) Deterrents most likely did not stop you (2) Deterrents probably stopped you (5) Deterrents definitely did not stop you (3) Uncertain if deterrents stopped you (0) Does not apply	—																		
Reasons for Ideation What sort of reasons did you have for thinking about wanting to die or killing yourself? Was it to end the pain or stop the way you were feeling (in other words you couldn't go on living with this pain or how you were feeling) or was it to get attention, revenge or a reaction from others? Or both?	(1) Completely to get attention, revenge or a reaction from others (4) Mostly to end or stop the pain (you couldn't go on living with the pain or how you were feeling) (2) Mostly to get attention, revenge or a reaction from others (5) Completely to end or stop the pain (you couldn't go on living with the pain or how you were feeling) (3) Equally to get attention, revenge or a reaction from others and to end/stop the pain (0) Does not apply	—																		

SUICIDAL BEHAVIOR (Check all that apply, so long as these are separate events; must ask about all types)		Since Last Assessment
Actual Attempt: A potentially self-injurious act committed with at least some wish to die, as a result of act. Behavior was in part thought of as method to kill oneself. Intent does not have to be 100%. If there is any intent/desire to die associated with the act, then it can be considered an actual suicide attempt. There does not have to be any injury or harm , just the potential for injury or harm. If person pulls trigger while gun is in mouth but gun is broken so no injury results, this is considered an attempt. Inferring Intent: Even if an individual denies intent/wish to die, it may be inferred clinically from the behavior or circumstances. For example, a highly lethal act that is clearly not an accident so no other intent but suicide can be inferred (e.g., gunshot to head, jumping from window of a high floor/story). Also, if someone denies intent to die, but they thought that what they did could be lethal, intent may be inferred. Have you made a suicide attempt? Have you done anything to harm yourself? Have you done anything dangerous where you could have died? What did you do? Did you _____ as a way to end your life? Did you want to die (even a little) when you _____? Were you trying to end your life when you _____? Or Did you think it was possible you could have died from _____? Or did you do it purely for other reasons / without ANY intention of killing yourself (like to relieve stress, feel better, get sympathy, or get something else to happen)? (Self-injurious Behavior without suicidal intent) If yes, describe: _____		Yes  No  Total # of Attempts _____
Has subject engaged in Non-Suicidal Self-Injurious Behavior? Interrupted Attempt: When the person is interrupted (by an outside circumstance) from starting the potentially self-injurious act (if not for that, actual attempt would have occurred). Overdose: Person has pills in hand but is stopped from ingesting. Once they ingest any pills, this becomes an attempt rather than an interrupted attempt. Shooting: Person has gun pointed toward self, gun is taken away by someone else, or is somehow prevented from pulling trigger. Once they pull the trigger, even if the gun fails to fire, it is an attempt. Jumping: Person is poised to jump, is grabbed and taken down from ledge. Hanging: Person has noose around neck but has not yet started to hang - is stopped from doing so. Has there been a time when you started to do something to end your life but someone or something stopped you before you actually did anything? If yes, describe: _____		Yes  No  Total # of interrupted _____
Aborted Attempt: When person begins to take steps toward making a suicide attempt, but stops themselves before they actually have engaged in any self-destructive behavior. Examples are similar to interrupted attempts, except that the individual stops him/herself, instead of being stopped by something else. Has there been a time when you started to do something to try to end your life but you stopped yourself before you actually did anything? If yes, describe: _____		Yes  No  Total # of aborted _____
Preparatory Acts or Behavior: Acts or preparation towards imminently making a suicide attempt. This can include anything beyond a verbalization or thought, such as assembling a specific method (e.g., buying pills, purchasing a gun) or preparing for one's death by suicide (e.g., giving things away, writing a suicide note). Have you taken any steps towards making a suicide attempt or preparing to kill yourself (such as collecting pills, getting a gun, giving valuables away or writing a suicide note)? If yes, describe: _____		Yes  No 
Suicidal Behavior: Suicidal behavior was present during the assessment period?		Yes  No 
Suicide:		Yes  No 
Answer for Actual Attempts Only		Most Lethal Attempt Date: _____ Enter Code _____
Actual Lethality/Medical Damage: 0. No physical damage or very minor physical damage (e.g., surface scratches). 1. Minor physical damage (e.g., lethargic speech; first-degree burns; mild bleeding; sprains). 2. Moderate physical damage; medical attention needed (e.g., conscious but sleepy, somewhat responsive; second-degree burns; bleeding of major vessel). 3. Moderately severe physical damage; medical hospitalization and likely intensive care required (e.g., comatose with reflexes intact; third-degree burns less than 20% of body; extensive blood loss but can recover; major fractures). 4. Severe physical damage; medical hospitalization with intensive care required (e.g., comatose without reflexes; third-degree burns over 20% of body; extensive blood loss with unstable vital signs; major damage to a vital area). 5. Death		Enter Code _____
Potential Lethality: Only Answer if Actual Lethality=0 Likely lethality of actual attempt if no medical damage (the following examples, while having no actual medical damage, had potential for very serious lethality: put gun in mouth and pulled the trigger but gun fails to fire so no medical damage; laying on train tracks with oncoming train but pulled away before run over).		Enter Code _____
0 = Behavior not likely to result in injury 1 = Behavior likely to result in injury but not likely to cause death 2 = Behavior likely to result in death despite available medical care		

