7.2. Treatment Period (12 Weeks)

Treatment Period must begin on the day after randomization. Study treatment will be blinded, and subjects will take one study tablet three times during the day, approximately 5 hours apart. Subjects randomly assigned to Arm A will take one placebo tablet at each dosing per day for 12 weeks. Arm B subjects will take one cytisinicline tablet at each dosing per day for the first 6 weeks followed by one placebo tablet at each dosing per day for the last 6 weeks. Arm C subjects will take one cytisinicline tablet at each dosing per day for 12 weeks.

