Use of any non-cigarette nicotine products ¹⁴						•	•	•	•	•	•	•	•	•	•	•	
Serum Cotinine	• ¹⁵					•		•		•		•		•	•		

¹Randomization *may* occur at the SV2 visit *IF* subject can commit to a quit date that allows start of treatment the following day. In such cases all Day 0 (Randomization) procedures must be completed at the SV2 clinic visit.

²Clinic will telephone each subject towards the end of Day 1 (first day of treatment) to make sure subject has taken medication according to dosing schedule, answer any questions, assess for adverse events and any concomitant medications.

³The final day of treatment should be on Day 84. In order to ensure subject completes all treatment prior to assessments, the W12 visit is to be scheduled on Day 86 ± 1 Day. If subject discontinues the study prior to Week 12, complete the planned 12-week assessments at the time of discontinuing, and record on the Early Discontinuation CRF.

⁴ The Screening assessment for suicidal ideation (questions 1-5) will be asked in the temporal context of “within the past 3 months” and the Suicidal Behavior questions will be asked within the temporal context of “within lifetime” in order to fully evaluate current ideation or risk of suicide. Assessments conducted at Week 6 and Week 12 will ask all questions in the temporal context of “since last assessment” for suicidal ideation/risk.

⁵Physical exam may be conducted at either the SV1 or the SV2.

⁶ Urine pregnancy test kits supplied to site by central laboratory. All other testing performed by a central laboratory. Test results must be negative at the SV1 and D0 visit for inclusion into the study, excluding females who are surgically sterile (hysterectomy or tubal ligation) or are >2 years post-menopausal.

⁷ Drugs of abuse to include at a minimum amphetamines, methamphetamines, barbiturates, benzodiazepines, cocaine, ecstasy, opiates, and phencyclidine.

⁸ To include height at screening for BMI calculation.

⁹ There are two distinct diaries to be used: The screening smoking diary will capture daily cigarette consumption for 7 consecutive days so that an average can be obtained to assess Inclusion Criteria #2. The on-study treatment diary is to assess treatment compliance and will capture each study drug dose date and time.

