APPENDIX 1. COLUMBIA - SUICIDE SEVERITY RATING SCALE (C-SSRS)

The Columbia Suicide Severity Rating Scale (C-SSRS) provides a standardized method to assess both suicidal ideation and behaviour to identify those at risk for suicide.²¹ The questionnaire must be administered by trained study staff* at Screening and again at the Week 6 (Day 42) and Week 12 (Day 86) study visits. Assessments at Screening will utilize the “Screening” version of the form with ideation to be assessed in the past 3 months and suicidal behaviour within lifetime (the later assessment timing helps to discern if later positive assessments are possibly treatment emergent). Any “Yes” to question 4 or 5 OR “Yes” to any suicidal behaviour question with clear suicidal intent or previous attempt will be considered exclusionary for this study. Assessments at Week 6 (Day 42) and Week 12 (Day 86) study visits will utilize the “Since Last Visit” version of the form with timeframe to be “since last assessment”. Any “Yes” to question 4 or 5 OR “Yes” to any suicidal behaviour question at the Week 6 (Day 42) or Week 12 (Day 86) study visits requires reporting as an AE as well as referral to a qualified Mental Health Professional for follow-up.

*Training by study staff is to be documented via certification in past 1 year on the C-SSRS. Training can be obtained on-line (www.cssrs.columbia.edu/training/training-research-setting).

COLUMBIA-SUICIDE SEVERITY RATING SCALE (C-SSRS)

Screening

Version 1/14/09

Posner, K.; Brent, D.; Lucas, C.; Gould, M.; Stanley, B.; Brown, G.; Fisher, P.; Zelazny, J.; Burke, A.; Oquendo, M.; Mann, J.

Disclaimer:

This scale is intended to be used by individuals who have received training in its administration. The questions contained in the Columbia-Suicide Severity Rating Scale are suggested probes. Ultimately, the determination of the presence of suicidal ideation or behavior depends on the judgment of the individual administering the scale.

Definitions of behavioral suicidal events in this scale are based on those used in The Columbia Suicide History Form, developed by [name] and [name], Conte Center for the Neuroscience of Mental Disorders (CCNMD), New York State Psychiatric Institute, [name]. (Oquendo M. A., Halberstam B. & Mann J. J., Risk factors for suicidal behavior: utility and limitations of research instruments. In M.B. First [Ed.] Standardized Evaluation in Clinical Practice, pp. 103 -130, 2003.)

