3.4. Safety Objectives

1. To evaluate the safety profile of 3 mg TID cytisinicline compared to placebo (Arm B vs Arm A; Arm C vs Arm A).
2. To compare the safety profiles of Arm B subjects versus Arm C subjects with respect to adverse events occurring after Week 6 on the study.

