6.4.2. Questionnaire Scoring

This section describes scoring for the questionnaires that will be used in the study. No imputation will be done for missing item responses on the questionnaires. Total scores will only be computed if there are no missing item scores.

Fagerstrom Test of Nicotine Dependence (FTND)

The FTND is a 6-item multiple-choice questionnaire (see Appendix 2 of the study protocol). It will be administered at SV1. An FTND total score will be derived for each subject providing all questions have been answered, using the scoring key that follows:

Item #	Item Text	Item Response	Item Score
1	How soon after you wake up do you smoke your first cigarette?	Within 5 minutes	3
		6–30 minutes	2
		31–60 minutes	1
		After 60 minutes	0
2	Do you find it difficult to refrain from smoking in places where it is forbidden (eg, in church, at the library, in the cinema, etc.)?	Yes	1
		No	0
3	Which cigarette would you hate most to give up?	The first one in the morning	1
		All others	0
4	How many cigarettes/day do you smoke?	10 or less	0
		11 – 20	1
		21 – 30	2
		31 or more	3
5	Do you smoke more frequently during the first hours after waking than during the rest of the day?	Yes	1
		No	0
6	Do you smoke if you are so ill that you are in bed most of the day?	Yes	1
		No	0

Smoking Self-efficacy Questionnaire (SEQ-12)

The SEQ-12 is a 12-item questionnaire that will be administered at the Day 0 visit. Item scores will be assigned using the scoring key pre-printed on the questionnaire (see Appendix 3 of the study protocol). Three scores will be derived for each subject providing there are no missing questions: SEQ-12 internal stimuli score (items 1-6), external stimuli score (items 7-12) and a total score (items 1-12).

Hospital Anxiety and Depression (HADS)

The HADS questionnaire will be administered at SV1, Week 6 and Week 12. Item scores will be assigned using the scoring key pre-printed on the questionnaire (see Appendix 6 of the study protocol). Providing there are no missing questions, total scores for depression and anxiety and overall will be derived for each subject.

Brief Questionnaire of Smoking Urges (QSU-Brief)

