- Incidence by SOC and preferred term (PT), in alphabetical order of SOC and PT, for both all TEAE and related TEAE
- Incidence by PT, in decreasing frequency of PT, for both all TEAE and related TEAE
- Incidence of TEAEs that resulted in dose reduction or discontinuation of study drug (ie, action taken with study drug reported as dose reduced, dose interrupted, or drug withdrawn), in decreasing frequency of PT
- Incidence of TEAE by PT and severity (mild, moderate, severe), in alphabetical order of PT

- Incidence of TEAE by PT and relationship (related, not related), in alphabetical order of PT
- Incidence of TEAE by PT for events of special interest: COVID-19

The following summaries will also be produced of TEAEs occurring after Week 6 (occurring after Week 6 or ongoing after Week 6) on the study (see definitions above):

- Incidence by SOC and PT, in alphabetical order of SOC and PT
- Incidence by PT, in decreasing frequency of PT
- Incidence of TEAEs that resulted in dose reduction or discontinuation of study drug (ie, action taken with study drug reported as dose reduced, dose interrupted, or drug withdrawn), in decreasing frequency of PT

The following will also be summarized:

- Incidence of TEAEs that occurred from Week 6 (approximately Study Day 42) visit + 1 day through Week 7 visit (approximately Study Day 49) will be assessed for any possible withdrawal effects when switching to placebo during the first Week 7 timeframe for the cytisinicline 6 weeks arm.
- Incidence of TEAEs by time of onset (Up to Week 6 [approximately Study Day 42] visit and after Week 6 visit through Last Dose)
- Incidence of TEAEs by primary endpoint status

In summaries of AE incidence, if a subject experiences the same AE (preferred term) multiple times that subject will be counted only once for that preferred term. Similarly, if a subject experiences multiple AEs (preferred terms) within the same SOC then that subject will be counted only once for that SOC. When summarizing by severity and relationship, only the AE with the highest severity or relationship will be counted.

A Kaplan-Meier figure of time to first TEAE (ie, time from date of randomization to earliest TEAE start date) will be provided by treatment arm. Subjects with no Adverse events will be censored at their last visit.

In addition to summary tables, the following listings will be produced.

- All AEs

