11.1.2. Other Adverse Events of Special Interest

Other adverse events of special interest were defined in Section 4.2.1.3 as the following events:

- treatment-emergent suicidal ideation or behavior
- treatment-emergent moderate to severe depression
- new pregnancy
- COVID-19

The number (%) of subjects with each event will be summarized by treatment arm.

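### The SAP counts C-SSRS suicidality and HADS depression events once per arm across the Week 6 switch, so the depression event is never tabulated after Week 6 for Arm B versus Arm C

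*Protocol*

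**What the plan says.** **Collection.** Protocol Appendix 1 requires the C-SSRS "at Screening and again at the Week 6 (Day 42) and Week 12 (Day 86) study visits". Footnote 4 to Table 4 (Protocol 12.1) sets the recall period: "Assessments conducted at Week 6 and Week 12 will ask all questions in the temporal context of" the interval since the last assessment. SAP 6.4.2 gives the HADS timing: "The HADS questionnaire will be administered at SV1, Week 6 and Week 12".

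**Treatment.** Protocol 7.2: "Arm B subjects will take one cytisinicline tablet at each dosing per day for the first 6 weeks followed by one placebo tablet" for the last six weeks. Arm C takes drug throughout.

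**Objective.** Safety objective 2 in SAP 3.4 reads "To compare the safety profiles of Arm B subjects versus Arm C subjects with respect to adverse events occurring after Week 6 on the study".

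**Event definitions and table.** SAP 4.2.1.3 defines the suicidality event (C-SSRS question 4 or 5, or any behaviour item) and the depression event (HADS depression score of 11 or more) by any qualifying result on or after first dose. SAP 11.1.2 then says "The number (%) of subjects with each event will be summarized by treatment arm". Neither section divides the events by visit or period.

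**Other planned outputs.**
- SAP 11.1 has overall and SOC/PT tables for AEs starting after Week 6, and a table by onset up to or after the Week 6 visit. Its special-interest line covers one condition: "Incidence of TEAE by PT for events of special interest: COVID-19".
- SAP 10.2.11 summarizes HADS, QSU-Brief and MNWS scores by arm and visit; C-SSRS is not among them.
- The by-visit safety outputs named in SAP 11 include neither C-SSRS nor HADS.

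**The concern.** At Week 6, Arms B and C have had the same planned treatment. At Week 12, Arm B has had six weeks of placebo and Arm C six more weeks of drug. The two on-study assessments therefore fall either side of the only point at which the arms diverge. A single ever-after-first-dose count removes that information: an Arm B subject first positive at Week 12, after six weeks of placebo, is indistinguishable from one positive at Week 6 on drug.

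Suicidality and depression are named by the sponsor as events of special interest, and safety objective 2 asks about the period after Week 6. A reader who wants to know whether the longer course, or the switch to placebo, changes these events cannot read it from the table designed to report them.

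**Working it through.** The plan states no figure on this point, so there is nothing to reproduce. The check has two parts.

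**1. Where does each event appear after Week 6, by arm?**

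| Event | SAP 11.1.2 | AE tables after Week 6 (SAP 11.1) | By-visit summary |
|---|---|---|---|
| Positive C-SSRS | Pooled only | Yes, through the AE report required by Protocol Appendix 1, placed by start date and coded term | None |
| HADS depression of 11 or more | Pooled only | No rule makes it an AE | Scores only (SAP 10.2.11), not the number at or above 11 |

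For depression, the score summary includes a maximum (SAP 6.2). It can show that at least one subject reached 11, but not how many.

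For suicidality, the AE route has a weak spot. SAP 6.4.1 imputes a missing or partial AE start date as the earliest possible date on or after first dose, and a wholly missing one as the first-dose date. An Arm B event first reported at Week 12 with no onset date would then be assigned to the drug period. Where a Week 6 form exists, the Week 12 form itself would place it after Week 6.

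**2. What does pooling do to the Arm B versus Arm C contrast?**

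Inputs: 250 per arm (SAP 2.1). The documents give no suicidality or depression rates, so every rate below is an assumption. Let p1 be the Weeks 1-6 risk (same in both arms) and qB, qC the risks after Week 6. If the two windows are independent within a subject:

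- pooled risk = 1 − (1 − p1)(1 − q)
- pooled difference = (1 − p1)(qC − qB)

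*Case 1: qB = 1%, qC = 2%; true ratio 2.00, true difference 1.0 point.*

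| p1 | Pooled ratio | Pooled difference (points) | Drug-period share of Arm B events, p1/(p1 + qB) |
|---|---|---|---|
| 0.5% | 1.67 | 1.00 | 33% |
| 1% | 1.50 | 0.99 | 50% |
| 2% | 1.33 | 0.98 | 67% |
| 4% | 1.19 | 0.96 | 80% |

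With the direction reversed (qB = 2%, qC = 1%), a ratio of 0.50 becomes 0.60, 0.67, 0.75 and 0.84.

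*Case 2: p1 = 4%, qB = 4%, qC = 8%.*
- Split: difference 4.00 points, SE = √[(0.04×0.96 + 0.08×0.92)/250] = 2.12 points, ratio of difference to SE 1.89.
- Pooled: Arm B 1 − 0.96² = 7.84%; Arm C 1 − 0.96×0.92 = 11.68%. Risk ratio 1.49, difference 3.84 points, SE 2.65 points, ratio of difference to SE 1.45.

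*Dependence.* If every subject positive in the first window stays positive in the second, pooled Arm B risk is p and pooled Arm C risk is 2p. The ratio stays 2.0 and nothing is lost. With equal risks in Weeks 1-6 and in Arm B afterwards, the pooled ratio therefore lies between about 1.5 (independence) and 2.0 (full persistence).

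**The case against.** A reader might infer that safety objective 2 goes unanswered for suicidality and depression. The documents do not support that.

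- The objective is worded in terms of adverse events. Protocol Appendix 1 makes a positive C-SSRS at Week 6 or Week 12 a reportable AE, and AEs are tabulated after Week 6 by arm. For suicidality the route is indirect, not absent.
- HADS depression scores are summarized by arm and visit, so scores are not pooled; only the threshold event is. Because no rule makes a score of 11 or more an AE, the objective as worded does not strictly call for it.
- SAP 6.2 plans listings by arm, subject and visit where appropriate, so the timing of rare events should be recoverable subject by subject.

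A reader might also infer that the forms separate drug from post-switch time cleanly. They do not.
- The Week 6 C-SSRS looks back to Screening, which may be up to 28 days before randomization.
- HADS as reproduced in Protocol Appendix 6 states no look-back period.
- The Week 12 visit is on Day 86 ± 1, after the last dose on Day 84, so Arm C has also just stopped.
- Subjects leaving the study early complete the Week 12 forms at that time, possibly before Week 6 (Protocol 8.3.2). Subjects who stop treatment but stay are assessed at end of treatment and again at Week 12 (SAP 4.2.1.4).
- A HADS score of 11 or more that begins on drug and persists would count again at Week 12 unless new onset is shown separately.

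Finally, counting a subject once is normal incidence reporting, and Arm B versus placebo over 12 weeks is a legitimate comparison of the randomized regimen. SAP 11 plans no safety tests.

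All of this stands, and it limits the point. It does not supply a post-Week-6 summary of the depression event, or explain why special-interest events lack the split given to ordinary AEs.

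**Conclusion.** The point holds as a gap in descriptive safety reporting. SAP 4.2.1.3 and 11.1.2 merge the Week 6 and Week 12 results for two named special-interest events, although the arms being compared diverge between those visits. For HADS depression of 11 or more, no planned summary table shows the event after Week 6 for Arm B versus Arm C. For suicidality, the answer depends on AE dating and coding.

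The size is modest. Under assumed rates, equal window risks and independent windows, a true ratio of 2.0 would appear as about 1.5; persistence within subjects reduces the dilution, and a higher Weeks 1-6 risk increases it. The absolute difference is almost unchanged (4.00 to 3.84 points in the larger example). Pooling hides timing and weakens the contrast; in these calculations it does not reverse it. No alpha, power or efficacy conclusion is involved. The change is worth making because it is cheap and serves an objective the trial set itself.

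**What to change.** In SAP 11.1.2, for the C-SSRS event and for HADS depression of 11 or more:

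1. Keep the pooled row as the overall count.
2. Add, by arm, a row for (a) assessments up to and including the Week 6 visit and (b) assessments after Week 6 through Week 12, each with the number of subjects assessed as denominator.
3. For (b), also show new-onset events (not positive at Week 6), and give the Arm C minus Arm B difference with a 95% CI labelled descriptive.
4. Assign each form to a period by its actual date and look-back rather than its visit label, so that early-discontinuation and end-of-treatment forms are placed correctly.
5. Show C-SSRS forms whose look-back spans the switch, such as a Week 12 form with no earlier on-study form at or near Week 6, in a separate row.

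The cost is one re-laid-out table and a short derivation rule, using data already collected. The downside is smaller counts per row, which for rare events will make the intervals wide.
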